8.1 Sample Size Considerations

The sample size of up to 8 subjects in Cohort 1 and up to 10 additional subjects in Cohort 2, is consistent with conventional first-in-human single and multiple ascending studies that generally enroll between 8-10 subjects per dose arm with escalation being based on safety and tolerability.

The sample size for the current study is not based on statistical testing of a formal powered hypothesis. The proposed clinical trial represents a re-purposing of CLTX-305, leveraging extensive exposure and safety data from the prior osteoporosis program, to conduct a modified single and multiple-ascending dose study in a new target population of subjects with ADH1. However, a recent publication of a different experimental calcilytic agent, NPSP795 (Roberts 2019), reported preliminary evidence for a dose-response on iPTH in subjects with ADH1 with a sample size of 5 subjects. The authors speculated that despite testing doses known to raise iPTH robustly in non-ADH1 subjects, larger doses would have been required to stimulate iPTH in ADH1 subjects sufficiently to also see elevations in cCa. The current protocol is designed to explore a broad potential dose range for safety and tolerability; however, the proposed sample size of approximately 16 subjects may be sufficient to confirm a definitive proof-of-concept on either iPTH and/or cCa if effective doses are achieved.

8.2 Randomization

This is an open-label non-randomized study and does not include treatment assignments.

9.0 Study Endpoints, Variables and Covariates

Objectives	Endpoints							
Primary								
 Periods 1, 2, and 3: Evaluate the safety and tolerability of single and multiple doses of CLTX- 305 (encaleret) in subjects with ADH1. 	 Periods 1, 2 and 3: Number of subjects with adverse events (AEs), serious AEs Absolute values and change from baseline in clinical safety (laboratory tests), vital signs, and electrocardiograms (ECGs). AEs and serious AEs (SAEs) – frequency count and percentages of subjects; Clinical safety laboratory tests, vital signs and ECGs – absolute levels and change from baseline. 							
 Period 3: Evaluate the safety, tolerability and efficacy of CLTX-35 (encaleret) in subjects with ADH1 after 24 weeks. 	 Period 3: cCa after treatment with CLTX-305 for 24 weeks - absolute levels and change from baseline. Urinary calcium clearance (fractional excretion) after treatment with CLTX-305 for 24 weeks – absolute levels and change from baseline; Urinary calcium clearance (24-hour total excretion) after treatment with CLTX-305 for 24 weeks - absolute levels and change from baseline. 							
 LTE: Evaluate the longer-term safety and tolerability of CLTX-305 (encaleret) in subjects with ADH1 from Period 3 for approximately 25 months (approximately 2 years). 	 LTE: AEs and SAEs - frequency count and percentages of subjects; Clinical safety laboratory tests and vital signs for approximately 25 months (approximately 2 years) - absolute levels and change from baseline. 							
Secondary								
 Periods 1 and 2: Evaluate the effect of CLTX-305 (encaleret) to increase serum iPTH levels after both single and multiple doses across a dose range in subjects with ADH1. 	 Periods 1, 2, and 3: Absolute values and change from baseline in iPTH blood concentrations profiles (24-hours) over time after single and multiple doses of CLTX-305 (encaleret). 							

Objectives	Endpoints							
Secondary								
 Evaluate the PK of both single and multiple ascending doses of CLTX- 305 in subjects with ADH1 where intensive PK sampling was done. 	• PK parameters: maximum plasma concentration (C_{max}) , time to maximum plasma concentration (t_{max}) , apparent terminal half-life $(t_{\frac{1}{2}})$, area under the concentration-time curve (AUC) from time 0 to the last measurable time point (AUC _{0-t}), AUC from time 0 to 24 hours (AUC _{2-cu}) AUC							
Period 1 (Day1, Day 2, Day 3 and Day 5) and Period 2 (Day 1 if CLTX dose is >	extrapolated to infinity (AUC _{0-inf}) following single- doses.							
180 mg BID and Day 5 regardless of dose received). Even though non- intensive sampling is performed at Period 3 Week 24; PK parameters will be derived at that visit.	- Determination of the steady state PK parameters: C_{max} , trough concentration (C_{trough}), and AUC over the dosing interval AUC _{0-tau} .							

Objectives		Endpoints							
Se	condary								
LT •	 E: Obtain long-term data on efficacy of CLTX-305 (encaleret) on blood calcium concentrations. Evaluate the long-term PD effects of CLTX-305 (encaleret) on associated measures of calcium homeostasis including, iPTH, 1.25-(OH)₂ Vitamin D levels and urinary calcium excretion. Evaluate the long-term PD effects of CLTX-305 (encaleret) on bone turnover markers including CTx and P1NP. 	 LTE: Endpoints measured over time up to 24 months (final visit): Blood calcium - absolute levels and change from baseline in cCa; Urinary calcium clearance (fractional excretion) - absolute levels and change from baseline; Urinary calcium clearance (24-hour total excretion) - absolute levels and change from baseline; Blood levels of iPTH - absolute levels and change from baseline; Blood levels of iPTH - absolute levels and change from baseline; Renal function (eGFR) - absolute levels and change from baseline; Serum levels of 1,25-(OH)₂ Vitamin D -Absolute levels and change from baseline; Blood samples for magnesium, phosphate, creatinine - absolute levels and change from baseline; Time-intervals for urine samples for pH, creatinine and cAMP (time-intervals) - absolute levels and change from baseline; Z4-hours urine samples for pH, magnesium excretion, potassium excretion, creatinine, phosphate excretion, sodium excretion and citrate – absolute levels and change form baseline; Fractional excretion for magnesium and tubular reabsorption of phosphate - absolute levels; Bone resorption markers (blood P1NP) - absolute levels and change from baseline; 							

10.0 Conventions and Derivations

10.1 Baseline

Baseline is defined as the last non-missing value before the first dose of study drug is administered to each subject. For subjects that are enrolled in either Period 1 and/or Period 2, baseline is the last non-missing value before the first dose of study drug in that period. For cohort 1 subjects, if there are no assessment performed prior to the first dose of Period 2, the baseline for Period 1 will be used as the baseline for Period 2. For Period 3 and LTE baseline is the same as the baseline for Period 2.

Laboratory parameters:

For the timed-intervals urine parameters, the baseline will be defined as follows:

• For the parameters collected as time-intervals (i.e. the results from samples collected at 15 minutes pre-dose, 0 to 4 hours, 4 to 8 hours, 8 to 13 hours, 13 to 17 hours and 17 to 24 hours), the baseline for Period 1 will be the 15 minutes pre-dose urine sample collected at Period 1 Day 1; the baseline for Period 2, Period 3 and LTE will be 15 minutes pre-dose urine sample collected at Period 2 Day 1.

• For the parameters collected on 0-24 hours, screening assessments will be considered as baseline (regardless of the laboratory analyzing the samples, local laboratories or NIH laboratory).

For chemistry parameters (serial sampling), the 15 minutes pre-dose samples on Day 1 from Period 1 will be the baseline for Period 1 and the 15 minutes pre-dose samples on Day 1 of Period 2 will be the baseline for Period 2. Screening values will be used for the count and percentage of subjects with a >50% decrease in 24-hr urine calcium excretion.

10.2 Change from Baseline

Change from baseline will be calculated as (value at post-baseline time point – value at baseline). Change from baseline will be calculated for subjects with both a baseline and post-baseline value as applicable. If a baseline or post-baseline value has not been recorded for a parameter, then change from baseline will not be calculated for that parameter. Subjects with missing change from baseline values will be excluded from descriptive statistics.

10.3 Derivations and Imputations

For laboratory data and for parameters that are continuous in nature but are reported as less than the lower limit of quantitation (LLOQ), lower than the limit of detection (LLOD) or above the upper limit of quantitation (ULOQ), the results will be imputed as follows:

- Results reported as '<xx' will be imputed as xx/2 (half of the numeric part).
- Results reported as '>xx' will be imputed as xx (numeric part).
- Results reported as '<LLOD' will be imputed as 0.

The following laboratory parameters will be derived:

• Estimated Glomerular Filtration Rate (eGFR) using CKD-EPI formula (mL/min/1.73m²) = $141 \text{ x min} (\text{SCr/K}, 1)^{\alpha} \text{ x max}(\text{SCR/K}, 1)^{-1.209} \text{ x } 0.993^{\text{Age}} \text{ x } 1.018 \text{ [if female] x } 1.159 \text{ [if Black]}.$

Where

SCr is the serum creatinine (mg/dL),

K = 0.7 for female and 0.9 for males,

 α is -0.329 for female and -0.411 for males,

Age (years) is the age at the sample collection date.

- **cCa (mg/dL)** = (0.8 * (4.0 Albumin [g/dL])) + Serum Calcium (mg/dL).
- **Fractional Calcium Excretion** at pre-dose, 0-4h, 4-8h, 8-13h, 13-17h, 17-24h intervals will be derived as follow.

 $(\text{Fractional Calcium Excretion})_{a-b} = \frac{(\text{Urine Calcium})_{a-b} \times (\text{Serum Creatinine})_b}{(\text{Serum Calcium})_b \times (\text{Urine Creatinine})_{a-b}}$

• **Fractional Magnesium Excretion** at pre-dose, 0-4h, 4-8h, 8-13h, 13-17h, 17-24h intervals will be derived as follow.

 $(\text{Fractional Magnesium Excretion})_{a-b} = \frac{[(\text{Urine Magnesium})_{a-b} \times (\text{Serum Creatinine})_b]}{0.7 \times [(\text{Serum Magnesium})_b \times (\text{Urine Creatinine})_{a-b}]} \times 100$

• **Tubular Reabsorption of Phosphorus** at pre-dose, 0-4h, 4-8h, 8-13h, 13-17h, 17-24h intervals will be derived as follow.

 $(\text{Tubular Reabsorption of Phosphorus})_{a-b} = \left[1 - \frac{(\text{Urine Phosphorus})_{a-b} \times (\text{Serum Creatinine})_b}{(\text{Serum Phosphorus})_b \times (\text{Urine Creatinine})_{a-b}}\right] \times 100$

Where

a-b is the interval considered (15 min pre-dose, 0-4h, 4-8h, 8-13h, 13-17h, 17-24h).

b is the end of the interval.

For Period 1 Day 5 and Period 2 Day 5, the 4, 8 and 15 hours post-evening dose blood sample results (i.e. serum results) will be used respectively, instead of the 13, 17 and 24 hours post-dose blood samples results.

For Period 1 Day 1 to Day 4 and Period 2 Day 1 to Day 4 and time-interval 17-24 hours, the 15 minutes pre-dose results from the following visit will be used (for example 15 minutes pre-dose Day 2 will be used to derive the 17-24 hours fractional excretion).

10.4 Study Day 1

For Period 1 assessments:

The day of the first dose of study drug in Period 1 is referred to as "Study Day 1".

For Period 2, Period 3 and LTE assessments:

The day of the first dose of study drug in Period 2 is referred to as "Study Day 1".

10.5 Study Day

For the considered period, Study Day is defined as the number of days from Study Day 1. If the day of interest is prior to Study Day 1, then Study Day is calculated as (Date of Interest – Date of Study Day 1). Therefore, the day prior to Study Day 1 is -1. If the day of interest is on or after Study Day 1, then Study Day is calculated as (Date of Interest – Date of Study Day 1, then Study Day is calculated as (Date of Interest – Date of Study Day 1) + 1.

10.6 Study / Treatment Completion

Cohort	Analysis Period	Start of the Period	End of the Period					
1	1	Earliest recorded medication	If the subject continued in Period 2: last dose in Period 1. If the subject did not continue in Period 2: all medications are assigned to Period 1.					
	2	Last dose date in Period 1 + 1 day	If the subject continued in Period 3: last dose in Period 2. If the subject did not continue in Period 3: Date of completion/discontinuation of the study.					

Cohort	Analysis Period	Start of the Period	End of the Period
	3	Last dose date in Period 2 + 1 day	If the subject continued in LTE: last dose in Period 3 If the subject did not continue in LTE: Date of completion/discontinuation of the study.
	LTE	Lase dose date in Period 3 + 1 day	Date of completion/discontinuation of the study.
2	2	Earliest recorded medication	If the subject continued in Period 3: last dose in Period 2. If the subject did not continue in Period 3: Date of completion/discontinuation of the study.
	3	Last dose date in Period 2 + 1 day	If the subject continued in LTE: last dose in Period 3 If the subject did not continue in LTE: Date of completion/discontinuation of the study.
	LTE Lase dose date in Period 3 + 1 day		Date of completion/discontinuation of the study.

A subject is considered to have completed the study if the answer is "YES" to the question "Did the subject complete the Study?" on the End of Study eCRF page. A subject is considered to have completed a period if the answer is "YES" to the question "Did the subject complete the Treatment Phase?" on the End of Treatment eCRF page for that period.

10.7 Prior and Concomitant Medications

As there will be no interruption of study drug treatment between Period 2, Period 3 and LTE, those 3 periods will be considered only one period and referred to Period 2 in the below definitions.

Prior Medications – Period 1

For subjects in cohort 1, prior medications or supplements will be any medications or supplements with a start date before the start of treatment on Study Day 1.

Prior Medications – Period 2

For subjects in cohort 1, prior medications or supplements will be any medications or supplements with a start date after the end of treatment from Period 1 and before the start of treatment in Period 2.

For subjects in cohort 2, prior medications or supplements will be any medications or supplements with a start date before the start of treatment on Study Day 1.

Concomitant Medications – Period 1

Concomitant medications are defined as any medications ongoing at the Period 1 start of treatment (i.e. medications which started before the Period 1 start of treatment and are recorded as ongoing or

with a stop date after the Period 1 start of treatment) or with a start date on or after the Period 1 start of treatment, but on or prior to the Period 1 end of study treatment + 30 days

Concomitant Medications – Period 2

Concomitant medications are defined as any medications ongoing at the Period 2 start of treatment (i.e. medications which started before the Period 2 start of treatment and are recorded as ongoing or with a stop date after the Period 2 start of treatment) or with a start date on or after the Period 2 start of treatment, but on or prior to end of study treatment + 30 days.

Each medication is mapped to a Period based on their start date and as per the rules defined in Table 1. If the start date is partial, determination of the Period will be based on the imputed start date (see Section 10.11 for details). If the date is entirely missing, the medication will be assigned to Period 1 for subjects in Cohort 1 and to Period 2 for subjects in Cohort 2.

Period	Prior	Concomitant
Period 1	Medications with start date/time	Medications with start date/time on or after Period 1 Day 1 and prior to the Period 2 Day 1 AM dose
	prior to Period 1 Day 1	Medications with start date/time prior to Period 1 Day 1 and end date/time on or after Period 1 Day 1/ongoing
Period 2/3	Medications with start date/time prior to the Period 2 Day 1 AM dose	Medications with start date/time on or after the Period 2 Day 1 AM dose and prior to the first dose in the LTE. If the participant does not continue into the LTE, then all medications with a start date on or after the Period 2 Day 1 AM dose will be mapped to Period 2/3.
		Medications with start date/time prior to the Period 2 Day 1 AM dose and end date/time on or after the Period 2 Day 1 AM dose/ongoing
LTE	Medications with start date/time prior to first dose in the LTE	Medications with start date/time on or after the first dose in the LTE.
		Medications with start date/time prior to the first dose in the LTE and end date/time on or after the first dose in the LTE/ongoing

Table 1: Mapping Rules of Medications to Each Period

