- If participant discontinues from the study early (ET) or withdraws from taking the CLTX-305 (encaleret) (EoT), perform related assessments, resume prior medication regimen, arrange FU labs within 1-2 days, and a FU call within 30 ± 7 days after last dose of the CLTX-305 (encaleret).
- 3. Outpatient laboratory testing includes blood Cr, Ca, Alb, Mg, PO4, iPTH, and PK sample collection on Day 7 or 8 after discharge from NIH CC on Day 6.
- 4. Including CaSR mutational analysis (if not documented).
- 5. Safety Labs Chemistry (Na, K, Cl, bicarbonate, Glu, BUN, Cr, Alb, total protein, Ca, Mg, PO4, iPTH, 25-OH Vitamin D, cholesterol, TG, AST, ALT, Tbili, Alk phos, LDH, amylase, lipase, uric acid), Hematology (RBC, Hgb, Hct, RBC indices, WBC, differential), Coagulation (PT/PTT/INR), urinalysis. HIV, viral hepatitis panel to be done at screening visit only.
- 6. Height measured at screening only.
- 7. Vital signs include supine or sitting blood pressure (BP) by automated cuff, heart rate (HR), and respiratory rate, to be collected q8 hours during in-patient days. Orthostatic BP and HR will be assessed once at screening and once daily during Period 1.
- 8. Discontinue calcitriol on Day -1 during the admission.
- 9. On Days 1, 2, & 3 participants receive CLTX-305 (encaleret) per the dosing algorithm. On Day 4 & 5 participants receive BID doses based on Days 1-3.
- 10. 24-hour urine at the screening visit and 10-14 days prior to Day 1 dosing (Ca, Mg, PO4, Cr, Na, K, Citrate, pH).
- 11. Outpatient laboratory testing on day -14-10 includes: blood Cr, calcium, albumin, magnesium, phosphate, 25-OH Vitamin D.
- 12. Interval lab tests at outpatient laboratory will be done in those for whom the screening visit is >21 days prior to Period 1.
- 13. After the last dose of CLTX-305 (encaleret), participants resume prior outpatient conventional treatment regimen prior to discharge.
- 14. Telephone contact: should occur on days 9 to 11 or once calcium results are available. PI/study staff to review results with participant.
- Telephone contact:  $30 \pm 7$  days after last dose of CLTX-305 (encaleret) in Period 1 to review AEs/Con meds

**Table B** Period 2 Schedule of Activities

	~			CC in						FU Post last
Period 2	Screening 	Interval Labs 11	Admission		B	ID Do	sing		Discharge/EoT/ET 	dose
Days	-60 to -2	-14 to -10	-1	1	2	3	4	5	6	
Informed Consent	X									
Admission to clinic	X		X							

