13.3.2 Concomitant Medications

Medications received either prior to or concomitantly with study drug will be categorized by Anatomical Therapeutic Chemical Classification (ATC) and preferred name (PN) according to World Health Organization (WHO) Drug dictionary (version 2021MAR01 Global B3 or later). Prior and concomitant medications will be included in a subject data listing, and tabulated separately for Period 1 and for all subjects in the Safety Analysis Set. The prior and concomitant medication tables will be sorted by descending frequency in the medication class, followed by descending frequency PN.

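### SAP 10.6, the 10.7 text and Table 1 classify a drug restarted after the last Period 1 dose differently, and the Period 1 concomitant table cannot separate on-treatment calcitriol from the planned restart

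*SAP*

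**What the plan says.** Three places in the SAP assign medications to periods.

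- **10.7 text.** A Period 1 concomitant medication is one ongoing at the first Period 1 dose, or one that starts from then and "on or prior to the Period 1 end of study treatment + 30 days". For Cohort 1, a drug is a Period 2 prior medication if it is recorded "with a start date after the end of treatment from Period 1 and before the start of treatment in Period 2".
- **Table 1**, which 10.7 names as the mapping rule. The first Period 1 concomitant entry is "Medications with start date/time on or after Period 1 Day 1 and prior to the Period 2 Day 1 AM dose". There is no 30-day limit. For participants who do not enter the LTE, "all medications with a start date on or after the Period 2 Day 1 AM dose will be mapped to Period 2/3".
- **The table under 10.6.** For Cohort 1 the end of Period 1 reads "If the subject continued in Period 2: last dose in Period 1", and Period 2 begins at "Last dose date in Period 1 + 1 day".

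SAP 13.3.2 has prior and concomitant medications listed by subject and "tabulated separately for Period 1 and for all subjects in the Safety Analysis Set".

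The protocol sets the timing. Calcitriol stops on Day -1, and the last Period 1 dose is given on the evening of Day 5 (8.2.1). Table A, footnote 13 then states: "After the last dose of CLTX-305 (encaleret), participants resume prior outpatient conventional treatment regimen prior to discharge". Section 8.2.1 places this on Day 6 for all participants, and section 2.1 names calcitriol among the items resumed. Section 8.5.7 permits one or two calcitriol doses for hypocalcemia during dosing.

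**The concern.** The trial examines encaleret given without calcitriol, so a reader of the Period 1 concomitant table will want to know how many participants needed calcitriol while on drug. The planned restart falls one day after the last dose and inside both 10.7 windows. A permitted on-treatment dose and the scheduled restart therefore add to the same row. The three rules also disagree with each other, so a programmer cannot satisfy all of them, and the content of the table depends on which one is followed.

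**Working it through.** There is no planned figure to reproduce. The check applies each date rule to the same record, with Day 1 as the first Period 1 dose.

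**Inputs**
- Last Period 1 dose: Day 5 (protocol 8.2.1)
- Restart of conventional therapy: Day 6 (protocol 8.2.1; Table A, footnote 13)
- Gap between Periods 1 and 2: 8 to 16 weeks (protocol 8.2.2), counted here from the last Period 1 dose
- Cohort 1 size: 5 to 8 (protocol 4.1)

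**Step 1: where each Period 1 window ends**
- 10.7 text: 5 + 30 = Day 35.
- Table 1: just before 5 + 7 × 8 = Day 61, or 5 + 7 × 16 = Day 117. That leaves 60 − 5 = 55 to 116 − 5 = 111 days after the last dose inside the window.
- 10.6 table: Day 5 for participants who continue. For those who do not, every medication is assigned to Period 1.

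**Step 2: three example start dates, for a Cohort 1 participant who continues**

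| Start | 10.7 text | Table 1 | 10.6 table |
|---|---|---|---|
| Day 3 (on treatment) | Period 1 concomitant | Period 1 concomitant; also Period 2/3 prior | Period 1 |
| Day 6 (planned restart) | Period 1 concomitant; also Period 2 prior | Period 1 concomitant; also Period 2/3 prior | Period 2 |
| Day 40 | Period 2 prior only | Period 1 concomitant; also Period 2/3 prior | Period 2 |

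Being concomitant in one period and prior to the next is not in itself a contradiction. The conflicts are that 10.6 puts the Day 6 record in Period 2 alone, and that the text and Table 1 disagree on Day 40.

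**Step 3: the calcitriol row in the Period 1 table.** Let n be the Cohort 1 size and k the number who took calcitriol between first and last dose. Assume that all n used calcitriol before the study and that each restart is a new record.
- Under the 10.7 text or Table 1 the row is n/n for every k: 8/8 for k = 0, 1, 2 or 8, and 5/5 for k = 0, 1, 2 or 5.
- With the window limited to first through last dose the row is k/n: 0/8, 1/8, 2/8 and so on.

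**Step 4: Period 2/3**
- Participants who do not enter the LTE restart oral calcium and active vitamin D after the last dose (protocol Table C, footnote 2). Table 1 maps those starts to Period 2/3 concomitant with no upper limit, whereas the 10.7 text stops at 30 days after the end of treatment.
- Protocol 8.2.3 lets a participant who reaches Week 24 before the LTE is in place stop encaleret and restart calcitriol. SAP 10.7 assumes that treatment is never interrupted between Period 2 and the LTE. Table 1 would therefore count this off-drug calcitriol as Period 2/3 concomitant, because it starts before the first LTE dose.

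**The case against.** The case for treating this as minor tidying is substantial, and most of it stands.

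- **The data are recoverable.** SAP 13.0 and 13.3.2 plan listings of all data, including medications by subject. Protocol 6.5 has site staff administer and record inpatient medications, and 8.5.7 provides a case report form that captures treatment of symptomatic hypocalcemia. With 5 to 8 participants and five supervised dosing days, on-treatment calcitriol can be read by hand if dates are recorded. A reader might infer that such use is concealed. The documents do not support that.
- **Efficacy results do not depend on the flag.** The primary efficacy analysis is at Week 24 of Period 3 (SAP 13.7.1), and the post-hoc tests cover Periods 2 and 3 (13.7.4). None uses the Period 1 concomitant class. A reader might infer bias in calcium or vitamin D results, but nothing in the plan leads there.
- **A 30-day tail is defensible.** It matches the treatment-emergent window in SAP 10.8. Drug is also still present on the morning of Day 6. With a half-life of 10 to 14 hours (protocol 8.2.1) and an assumed 12 to 15 hours since the last dose, the fraction remaining runs from 0.5^(15/10) = 0.35 to 0.5^(12/14) = 0.55. It would be wrong to read the number of off-drug days in a window as a measure of misclassification.
- **Calcium is a different case.** Supplements are stopped or reduced from Day 1 and may properly continue (protocol 2.1, 6.5). Only calcitriol is stopped outright.
- **Table 1 is the named mapping rule**, so 10.6 could be regarded as subordinate.

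The last point does not remove the conflict. Table 1 contradicts the 30-day limit in the text of its own section. For adverse events the SAP handles the same gap differently: it ends Period 1 at last dose plus 30 days and lists later events separately (10.8, Table 2; 13.6.1).

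**Conclusion.** The inconsistency is real and follows from the stated rules. One Day 6 record receives different assignments under 10.6 and 10.7, and any start between Day 36 and the first Period 2 dose is treated differently by the 10.7 text and Table 1. As planned, the Period 1 concomitant table cannot separate permitted on-treatment calcitriol from the scheduled restart.

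The size is limited to summary tables. The n/n result rests on two assumptions that the documents do not settle: that every Cohort 1 participant had calcitriol in the prior regimen, and that the restart is entered as a new record. If a held drug stays as one open record, limiting the window to the dosing days would not separate it either. The Period 2/3 extension follows from the same rules, but its size is unknown. The documents do not say how many participants declined the LTE or waited for it, and SAP 13.7.1 reports no early discontinuations. The text of SAP 10.13 and 10.15 was not available, so any special handling there is outside this check.

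**What to change.** Align the 10.6 table, the 10.7 text and Table 1 on one rule, with the post-treatment limit in Table 1 set to last dose plus 30 days, as the 10.7 text already has it. Replace the no-interruption premise in 10.7 so that a stop while waiting for the LTE closes a treatment block.

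In the medication tables, separate drugs taken between the first and last encaleret dose of each block from drugs started after the last dose. Show calcitriol and other active vitamin D, and calcium, by this split. State how a held and resumed drug is recorded, since the split depends on it.

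The cost is SAP wording and one derived variable, with no new data collection. The downside is one extra category in the medication tables.
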